#### 2.2.8.6 Hyperglycemia events

The PI3K/AKT pathway plays a significant role in regulating glucose metabolism, particularly by regulating glucose transport into adipocytes and muscle tissue. Therefore, hyperglycemia is considered as an “on target” effect of BKM120. Regular monitoring of FPG, HbA1c, and insulin C-peptide is implemented in BKM120 protocols to evaluate this pharmacodynamics effect. Transient increases of plasma glucose levels have been reported commonly in patients treated with BKM120. Hyperglycemia observed at 100 mg/day, regardless of study drug relationship, in ongoing BKM120 studies are summarized in Table 5.

**Table 5 Number (%) of patients with Hyperglycemia (narrow search), regardless of study drug relationship, by preferred term and treatment occurred at 100 mg / day in ongoing BKM120 studies**

Study Number (n= number of patients treated with 100 mg/d BKM120)	All grades n (%)	Grade 3/4 n (%)
Single agent studies		
CBKM120X2101 (n=55)	19 (34.5%)	4 (7.3%)
CBKM120X1101 (n=9)	3 (33.3%)	1 (11.1%)
CBKM120C2201 (n=70)	40 (57.1%)	16 (22.9%)
CBKM120D2201 (n=38)	12 (31.6%)	6 (15.8%)
Combination studies		
CBKM120X2107 (phase I n=12)	6 (50.0%)	3 (25.0%)
CBKM120X2107 (phase II n=53**)	16 (30.2%)	3 (5.7%)
CBEZ235A2118 (n=22)	6 (27.3%)	2 (9.1%)
CBKM120B2101 (n=16)*	2 (12.5%)	0

These numbers include multiple event terms of a similar meaning to “hyperglycemia”: SMQ Hyperglycemia/new onset diabetes mellitus (narrow scope)

\*Data corresponding to MTD defined to be 70mg QD (in this study no patient was treated with BKM120 at 100mg)

\*\* This number includes 3 patients who were treated with trastuzumab but did not receive treatment with BKM120.

The highest rate of hyperglycemia (57.1%) was reported in [CBKM120C2201], a Phase II study conducted in patients with advanced endometrial carcinoma, as this was the only study among those listed allowing the enrollment of patients with controlled diabetes mellitus.

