However, so far, there were only two patients that experienced a grade 4 hyperglycemia, and they both were treated at the highest dose level (150mg/day) in [CBKM120X2101] study. In order to mitigate the potential risk of developing uncontrolled hyperglycemia, only patients with normal glycaemia defined as fasting plasma glucose (FPG)  $\leq$  120 mg/dL are eligible for study entry. Patients who have a poorly controlled diabetes mellitus defined as (HbA1c  $>$ 8%) are excluded. In addition, detailed guidelines to monitor patients are recommended including: regular monitoring of FPG to early identify hyperglycemia and prevent

acute/sub-acute complications, caution warranted for patients with history of DM, or taking corticosteroids, or with other severe medical conditions (e.g. infections). Hyperglycemia management guidance also includes: dietetic measures and appropriate anti-diabetic medications as per investigator's decision and/or local guidelines, consider oral anti-diabetics such as metformin as first-line treatment for sustained and more severe hyperglycemia (other drugs as appropriate), if sulfonylurea or insulin are initiated, patients should be instructed on how to recognize (and treat) hypoglycemia, for patients with history of DM, management should be based on prior anti-DM treatment. Detailed guidelines to monitor and manage patients who develop hyperglycemia are provided in Table 5.

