  - Myocardial infarction within the last 6 months, documented by persistent elevated cardiac enzymes or persistent regional wall abnormalities on assessment of LVEF function
  - History of documented congestive heart failure (New York Heart Association functional classification III-IV)

- Documented cardiomyopathy
12. Patient has poorly controlled diabetes mellitus or steroid-induced diabetes mellitus
  13. Other concurrent severe and/or uncontrolled concomitant medical conditions (e.g., active or uncontrolled infection) that could cause unacceptable safety risks or compromise compliance with the protocol
    - Significant symptomatic deterioration of lung function. If clinically indicated, pulmonary function tests including measures of predicted lung volumes, DLco, O2 saturation at rest on room air should be considered to exclude pneumonitis or pulmonary infiltrates.
  14. Impairment of gastrointestinal (GI) function or GI disease that may significantly alter the absorption of BKM120 (e.g., ulcerative diseases, uncontrolled nausea, vomiting, diarrhea, malabsorption syndrome, or small bowel resection). Patients with unresolved diarrhea will be excluded as previously indicated
  15. Patients who are currently receiving treatment with medication with a known risk to prolong the QT interval or inducing Torsades de Pointes and the treatment cannot either be discontinued or switched to a different medication prior to starting study drug. Please refer to Table 18 for a list of prohibited QT prolonging drugs with risk of Torsades de Pointes.
  16. Patients receiving chronic treatment with steroids or another immunosuppressive agent.
    - **Note:** Topical applications (e.g. rash), inhaled sprays (e.g. obstructive airways diseases), eye drops or local injections (e.g. intra-articular) are allowed. Patients with previously treated brain metastases, who are on stable low dose corticosteroids treatment (e.g dexamethasone 2 mg/day, prednisolone 10 mg/day) for at least 14 days before start of study treatment are eligible.
  17. Patients who have taken herbal medications and certain fruits within 7 days prior to starting study drug. Herbal medications include, but are not limited to St. John's wort, Kava, ephedra (ma huang), ginkgo biloba, dehydroepiandrosterone (DHEA), yohimbe, saw palmetto, and ginseng. Fruits include the CYP3A inhibitors Seville oranges, grapefruit, pummelos, or exotic citrus fruits.

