**Table 9: Criteria for Defining Dose-Limiting Toxicities**

TOXICITY	ANY OF THE FOLLOWING CRITERIA
Hematologic a	≥ CTCAE grade 3 neutropenia for > 7 consecutive days
	CTCAE grade 3 thrombocytopenia for > 7 consecutive days
	CTCAE grade 4 thrombocytopenia
	Febrile neutropenia (ANC < 1.0 x 10  /L, fever ≥ 38.5°C)
Renal	Serum creatinine ≥ 2.0 x ULN to ≤ 3.0 x ULN for > 7 consecutive days
	> CTCAE grade 3 serum creatinine
Hepatic b	Total bilirubin ≥ 2xULN to ≤ 3.0 x ULN for > 7 consecutive days
	> CTCAE grade 3 total bilirubin
	CTCAE grade 3 AST or ALT for > 7 consecutive days
	CTCAE grade 4 AST or ALT
Endocrine	Grade 2 hyperglycemia (confirmed with a repeat FPG within 24 hours) that does not resolve to grade 0 within 14 consecutive days (after initiation of glimepiride, metformin or glibenclamide)
	≥ Grade 3 hyperglycemia (confirmed with a repeat FPG within 24 hours)
Metabolic/Laboratory	CTCAE grade 3 asymptomatic amylase and/or lipase, not reversible to ≤ CTCAE grade 2 for > 7 consecutive days
	CTCAE grade 4 asymptomatic amylase and/or lipase
Pancreatitis	≥ CTCAE grade 2
Cardiac	Cardiac toxicity ≥ CTCAE grade 3 or cardiac event that is symptomatic or requires medical intervention
	Clinical signs of cardiac disease, such as unstable angina or myocardial infarction, or Troponin ≥ CTCAE grade 3
Neurotoxicity	≥ 1 CTCAE grade level increase
Mood alteration	CTCAE grade 2 mood alteration that does not resolve to ≤ grade 1 within 14 days despite medical treatment (for Anxiety only, if worsened from baseline)
	≥ CTCAE grade 3 mood alteration
Dermatologic	Any phototoxicity ≥ CTCAE grade 2, or skin toxicity (rash) resulting in interruption of BKM120 for > 21 consecutive days
Other adverse events	≥ CTCAE grade 3 adverse events (excluding ≥ CTCAE grade 3 elevations in

	alkaline phosphatase)
	≥ CTCAE grade 3 vomiting or CTCAE grade 3 nausea despite the use of standard anti-emetics
	≥ CTCAE grade 3 diarrhea despite the use of optimal anti-diarrhea treatments
	CTCAE grade 3 fatigue (asthenia) for > 7 consecutive days CTCAE grade 4 fatigue (asthenia)

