
Grade 2 (>160 – 250 mg/dL) [> 8.9 - 13.9 mmol/L]
	
 
• If signs or symptoms of hyperglycemia (for example, mental status changes, excessive thirst, polyuria) manage as for Grade 3 hyperglycemia (see below).
 
• If asymptomatic, maintain dose and re-check FPG within 24 hours. If grade worsens or improves then follow specific grade recommendations. If FPG remains at Grade 2:               
 
• maintain dose level and monitor FPG at least weekly until FPG resolves to ≤ Grade 1
 
• initiate or intensify medication with appropriate anti-diabetic treatment such as metformin; consider adding a second oral agent if no improvement after several days
 
• instruct patient to follow dietary guidelines according to local and/or institutional standards for management of diabetes mellitus (such as those provided by the American Diabetes Association) during the study
 
• If FPG does not resolve to ≤ Grade 1 within 14 days after institution of appropriate anti-diabetic treatment reduce BKM120 by 1 dose level
 
 
 
 
Continue with anti-diabetic treatment and check FPG at least weekly for 8 weeks, then continue checking at least every 2 weeks

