Grade 1 (> ULN - 160 mg/dL) [ > ULN - 8.9 mmol/L]	
Maintain dose level, check FPG every week
 
 
initiate or intensify medication with appropriate anti-diabetic treatment as per investigator's discretion
 
instruct patient to follow dietary guidelines according to local and/or institutional standards for management of diabetes mellitus (such as those provided by the American Diabetes Association) during the study
 
Consider use of oral anti-hyperglycemic therapy such as metformin (or intensify existing medications)
 
Check FPG at least weekly for 8 weeks, then continue checking at least every 2 weeks
 

Grade 2 (>160 - 250 mg/dL) [ 8.9 - 13.9 mmol/L]	
 
If signs or symptoms of hyperglycemia (for example, mental status changes, excessive thirst, polyuria) manage as for Grade 3 hyperglycemia (see below).
 
If asymptomatic, maintain dose and re-check FPG within 24 hours. If grade worsens or improves then follow specific grade recommendations. If FPG remains at Grade 2: 
 
maintain dose level and monitor FPG at least weekly until FPG resolves to ≤ Grade 1
 
initiate or intensify medication with appropriate anti-diabetic treatment such as metformin; consider adding a second oral agent if no improvement after several days
 
instruct patient to follow dietary guidelines according to local and/or institutional standards for management of diabetes mellitus (such as those provided by the American Diabetes Association) during the study
 
If FPG does not resolve to ≤ Grade 1 within 14 days after institution of appropriate anti-diabetic treatment reduce BKM120 by 1 dose level
 
 
 
Continue with anti-diabetic treatment and check FPG at least weekly for 8 weeks, then continue checking at least every 2 weeks
 

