### Drugs to be used with caution

Preliminary in vitro metabolism studies suggest that BKM120 is a weak, reversible inhibitor CYP3A4/5 ( $K_i=13.6 \mu\text{M}$ ,  $[I]/K_i=0.4$  where  $[I]$  is the average  $C_{\text{max}}$  at steady-state following 100 mg daily dose) and a weak reversible inhibitor of CYP2C8/2C9/2C19 ( $IC_{50}=34 \mu\text{M}$ ,  $[I]/IC_{50}=0.15$ ). Note: that with the data available, we are not able to confirm whether such interactions will occur in patients. Therefore, investigators, at their discretion, may administer concomitant medications known to be metabolized by CYP3A4/5, CYP2C8, CYP2C9 and CYP2C19. Patients receiving such medications must be carefully monitored for potentiation of toxicity due to any individual concomitant medications, and may require dose titration or reduction of the drug substrate. Please refer to Table 19 for a list of CYP450 substrates and carefully consider their co-administration with BKM120.

Particularly, caution is advised when BKM120 is co-administered with:

- Drugs which are substrates for CYP3A4, CYP2C8, CYP2C9 or CYP2C19 and which have a narrow therapeutic index.
- Oral anti-diabetics which are metabolized by CYP2C8 or CYP2C9 can possibly result in hypoglycemia. Patients who develop diabetes mellitus during the study should be treated according to the American Diabetes Association guidance. It is recommended that treatment start with metformin.
- If a patient, after study enrollment, requires the concomitant use of any QT prolonging medication with a possible or conditional risk for torsade de pointes then the investigators, at their discretion, may co-administer such medications. Patients receiving such medications must be monitored. Refer to Table 18 for a list of QT prolonging medications to be used with caution.

Note: please refer also to Table 18 for a list of **prohibited** QT prolonging medication.

- Please refer to Table 19 for a list of CYP450 substrates and carefully consider their co-administration with BKM120.
- Concomitant treatment with corticosteroids and BKM120 should be avoided, whenever possible, during this study. A short duration (< 2 weeks) of systemic corticosteroids is allowed (e.g. for chronic obstructive pulmonary disease, or as an anti-emetic). Chronic dosing of corticosteroids is known to induce CYP3A enzymes, thereby increasing the risk or reducing BKM120 overall exposure to sub-therapeutic levels.

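### Table 9 ties the persistent grade 2 hyperglycemia DLT to three named drugs, so a first asymptomatic event managed without them can require a dose reduction yet, read literally, not be a DLT

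*Combined protocol and SAP*

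**What the plan says.** Section 5.3 makes the DLT the basis for the MTD, which section 13 names as the primary endpoint. The Endocrine row of Table 9 (section 5.5) makes confirmed grade 2 hyperglycemia a DLT when it has not returned to grade 0 within 14 consecutive days, with the qualifier "after initiation of glimepiride, metformin or glibenclamide". The list carries no sign that these are examples, and insulin is not on it.

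Table 11 (section 6, FPG grade 2, printed twice) is drug-neutral. For asymptomatic grade 2 it keeps the BKM120 dose and tells the site to "initiate or intensify medication with appropriate anti-diabetic treatment such as metformin; consider adding a second oral agent if no improvement after several days". If FPG is not down to grade 1 or lower, the action is set "within 14 days after institution of appropriate anti-diabetic treatment reduce BKM120 by 1 dose level".

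Other places bear on which drug a patient receives:

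- Section 7.1.1.4 foresees an insulin regimen under an endocrinologist and sets no grade limit in that item.
- Section 2.2.8.6 says that "for patients with history of DM, management should be based on prior anti-DM treatment". Such patients can enter, because exclusion 12 in section 3.3 reads only "Patient has poorly controlled diabetes mellitus or steroid-induced diabetes mellitus".
- Pointing the other way, section 2.2.8.6 advises sites to "consider oral anti-diabetics such as metformin as first-line treatment", and Appendix B (drugs to be used with caution) adds: "It is recommended that treatment start with metformin".

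The mood row of Table 9 has the same 14-day structure but refers to medical treatment in general and names no drug.

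**The concern.** One table decides whether a patient counts toward the MTD, and the other decides whether that patient's dose is cut. They start from different treatments. Two patients at the same dose with the same glucose course can therefore be classed differently because of the rescue drug chosen, which says nothing about how well BKM120 was tolerated.

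The protocol calls hyperglycemia an on-target effect of BKM120 (section 2.2.8.6), so this is a central toxicity. Section 2.2.8.6 also explains the highest hyperglycemia rate among the listed studies (57.1%) "as this was the only study among those listed allowing the enrollment of patients with controlled diabetes mellitus". Patients with a history of diabetes are the ones whom that section steers toward prior treatment and not necessarily a new listed drug. Taken alone, the drug list can only leave events out of the DLT count. In a 3+3 design a single patient can settle a cohort.

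**Working it through.** **1. The text, worked through for two patients.** Suppose both are at dose level 4 (60 mg). Each has a first, confirmed, asymptomatic grade 2 event, still grade 2 at day 14 and not attributed to another cause. Patient A newly starts metformin. Patient B is given only insulin.

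| Rule | A | B |
|---|---|---|
| Table 11: above grade 1 at 14 days | reduce 60 to 40 mg | reduce 60 to 40 mg |
| Table 9, grade 2 hyperglycemia row | met | listed drug never initiated: literally not met |
| Table 9, grade 3 or higher rows | no | no |
| Table 9 note: more than 7 doses interrupted | no, dosing continues (section 5.5) | no |
| Table 9 note: second occurrence with a reduction within 28 days of first dose | no, first event | no |
| Section 6: hold at 20 mg | not reached | not reached |
| Counted in Table 7 | yes | no |

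The result for B is the same whether the parenthesis is a condition or only the start of the 14-day clock, since either way a listed drug has to be initiated.

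The qualifiers matter:

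- Symptomatic grade 2 is managed as grade 3 with BKM120 omitted, so the rule on more than 7 doses could apply.
- At level -1 (20 mg) the drug is held, not reduced. At levels 1 to 3 one reduction goes from 40 to 20 mg, so a hold can follow if the event persists. At levels 4 to 6 one reduction leads to 40, 60 or 80 mg.

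**2. The plan's own figure.** Under Table 7 the probability of escalation at DLT rate p is (1−p)³ + 3p(1−p)⁵. At p = .30 this is .343 + .151 = .494, matching .49 in section 13. The other four entries (.71, .31, .17, .08) also reproduce.

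**3. Illustration of undercounting.** The documents give no rate for uncounted events. Table 5 reports only all grades and grade 3/4. It does not separate grade 2 from grade 1, and it gives neither duration nor rescue drug. Assume a full DLT rate of 30% of which m is uncounted:

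| m (assumed) | Counted rate | P(escalate) |
|---|---|---|
| 0 | .30 | .494 |
| .01 | .29 | .358 + .157 = .515 |
| .02 | .28 | .373 + .163 = .536 |
| .05 | .25 | .422 + .178 = .600 |

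This is about 2 points of escalation probability per uncounted point.

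**4. If one such patient occurs.** Assume exactly one uncounted patient among the first three, with counted-DLT rate p in the others. Counting that patient turns escalation into stopping in two ways:

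- The other two have no DLT, and at least one of the three added patients does: (1−p)²[1−(1−p)³].
- Exactly one of the other two has a DLT, and three added patients would have had none: 2p(1−p)(1−p)³.

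The sums are:

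- p = .10: .220 + .131 = .351
- p = .20: .312 + .164 = .476
- p = .30: .322 + .144 = .466

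These are conditional on the event. With m of .01, .02 or .05, the chance of exactly one such patient in three is 3m(1−m)², or .029, .058 or .135.

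**The case against.** The strongest reply is that the parenthesis merely anchors the clock for the expected oral rescue and was never meant to be exhaustive. Metformin is the default first drug throughout, and section 5.5 itself speaks of appropriate co-medication. That may well be the intent, and the neutral mood row supports it. It does not rescue the wording, because a site applying the row as printed has no clock to start for a patient on insulin alone.

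Several limits stand in full:

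- Reach is narrow. Entry FPG must be 120 mg/dL or lower (section 3.2), and the event must be confirmed, asymptomatic, unresolved at 14 days and managed without starting a listed drug.
- Section 5.5 excludes events attributed to concomitant medications, and dexamethasone is given with cisplatin (section 5.8.2). Some events would go uncounted whatever the rescue drug.
- Section 5.3 bases the review before escalation on adverse events, examination and laboratory results. Section 5.5 requires review of grade 2 or higher events before a higher level opens, and section 5.3 leaves escalation to the principal investigator's discretion. A persistent event with a dose cut should be seen, even though its DLT status does not change.
- The same row demands return to grade 0, where Table 11 accepts grade 1. That counts more events than Table 11 acts on, so the net direction of the whole row is unknown.

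A reader might infer that every insulin-treated patient escapes the row. That is not so: insulin added after newly started metformin still leaves a listed drug initiated. If a listed drug was already in use before the event and is only intensified, the text is ambiguous, not clearly a non-DLT.

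**Conclusion.** The point holds as an inconsistency of wording on the primary endpoint. Tables 9 and 11 treat the same event by different treatment criteria, and a narrow group of patients can have a dose reduction for persistent grade 2 hyperglycemia without meeting the DLT row as printed. None of the other DLT rules reliably picks up a first asymptomatic event.

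The size cannot be derived from the documents. The .51 to .60 figures rest on an assumed 30% full DLT rate, assumed uncounted shares and mechanical use of Table 7. The .35 to .48 figures also assume that the case has already occurred. A reader might conclude that the MTD will be set too high, or that the 57.1% rate in section 2.2.8.6 measures the problem. Neither is supported. That rate covers all grades at 100 mg in an endometrial carcinoma study, and the safety reviews stand between a missed DLT and an escalation. The correction is worth making because it costs almost nothing, not because a large effect has been shown.

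**What to change.** In the Endocrine row of Table 9, replace the parenthesis with: *(after initiation or intensification of appropriate anti-diabetic treatment, including insulin)*. This matches Table 11 and the drug-neutral mood row, and leaves the choice of drug with the clinicians. There is no need to go further and fix the clock at the first dose adjustment with no restart. That would start the 14 days earlier for some patients and so change the DLT threshold itself.

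The cost is one wording change by amendment. No new data are needed: FPG is measured at every scheduled treatment visit (study calendar, section 10), and section 5.10 already requires medication changes to be recorded. The downside is that possibly a few more DLTs would be counted.
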